4.1 Recruitment and retention

Number of patients assessed for eligibility; number of patients who were excluded (with a tabulation of reasons for exclusion); number of patients who were randomised; number of randomised patients who withdrew consent including to use of data; number of patients allocated to each treatment arm; number of patients who completed follow-up to 12 months (or who died) with a tabulation of reasons for discontinuing early; number of patients included in analysis of primary outcome, by allocated treatment and overall. Person-years of follow-up for patients included in analysis of primary outcome by treatment arm, with proportion of this time that was after the start of the COVID-19 pandemic.

Graph of cumulative number randomised over time.

Dates of first and last patients randomised.

A tabulation of numbers of patients randomised by study site, split by allocated treatment (and overall), to show balance by this stratification factor.

4.2 Baseline characteristics

The following baseline characteristics are to be tabulated by allocated treatment, and overall. No formal statistical testing of the baseline characteristics will be performed. The first relevant observation will be presented if more than one observation was collected

Age at randomisation (years) [continuous, and as <65 or ≥65], Sex [binary], GRACE score [continuous, and using groups of <109, 109-139, 140 or more], Elevated first cardiac troponin [Y/N], Previous CAD [Y/N], Result from first ECG [categorical], Rhythm on first ECG [categorical], Admission at site with on-site invasive coronary angiogram facilities [Y/N].

Admission: Mode of presentation [categorical], Initial area of assessment [categorical]

Primary presenting complaint: Presenting complaint [categorical], Time from first onset of presenting complaint to randomisation [calculate in hours, present in days, continuous], Type of pain [categorical], Pattern of pain [categorical], Location of pain [categorical], Any radiation of pain [Y/N], Radiation to areas of the body [each a separate Y/N variables], Any aggravating factors [Y/N], Detailed aggravating factors [each a separate Y/N variable]; Any relieving factors [Y/N], Detailed relieving factors [each a separate Y/N variable]

Risk factors: Diabetes mellitus [Y/N], Hypertension [Y/N], Hyperlipidaemia [Y/N], Smoking [categorical], Cocaine abuse [Y/N], First degree relative with CAD onset aged <60 [Y/N], Killip classification [categorical], Body Mass Index (kg/m²) [continuous]

Past history of coronary artery disease: Previous MI [Y/N], Angina with positive diagnostic test [Y/N], Previous CABG [Y/N], Previous angiography [Y/N], Stenosis >50% on previous angiography [Y/N], Previous coronary angioplasty/PCI [Y/N], Previous CTCA [Y/N], Known CAD on CTCA [Y/N], Unproven Clinical label of CAD [Y/N].

Other comorbidities/past medical history: Other structural heart disease [Y/N], Chronic heart failure [Y/N], Cerebrovascular disease [Y/N], Peripheral vascular disease [Y/N], Malignancy [Y/N], Chronic obstructive pulmonary disease [Y/N], Asthma [Y/N], Chronic renal failure/chronic kidney disease [Y/N], Liver cirrhosis [Y/N], Chronic infectious disease [Y/N].

Routine admission blood tests: Urea (mmol/L) [continuous], Creatinine (μmol/L) [continuous], Estimated glomerular filtration rate (ml/minute/1.73m²) [categorised], Alanine aminotransferase (Units/L) [continuous], Haemoglobin (g/L) [continuous], White blood cell count (x10⁹/L) [continuous], Random blood glucose (mmol/L) [continuous], Cholesterol (mmol/L) [continuous].

Observations within 60 minutes prior to randomisation: Respiratory rate (breaths per minute) [continuous], Oxygen saturation (SpO₂ %) [categorical], Fraction inspired oxygen (%) [categorical], Heart rate (beats per minute) [continuous], Systolic blood pressure (mmHg) [continuous], Diastolic

Statistical Analysis Plan	RAPID-CTCA
Version No	2.0
Date Finalised	19 Aug 2020

blood pressure (mmHg) [continuous], Capillary blood glucose (mmol/L) [continuous], Temperature (°C) [continuous].

Treating clinical impression at time of randomisation: ACS [categorical], Diagnosis [categorical], Diagnosis certainty ((0-10 where 0 is the least certain and 10 is the most certain) [continuous]

Concomitant medication: Beta blocker, Calcium channel blocker, ACE Inhibitor or ARB, Nicorandil, Oral nitrate, Buccal or sublingual nitrate, Oral hypoglycaemic, Insulin, Statin, Aspirin, Clopidogrel, Prasugrel, Ticagrelor, TNK/TPA, LMWH, Tirofiban or equivalent 2B3A inhibitors, Intravenous nitrate (including infusion), Fondaparinux, Unfractionated heparin, Bivalirudin, Novel anticoagulants, Intravenous morphine/opiate, Diuretic, Proton Pump Inhibitor, Ivabradine, Warfarin, Ranolazine.

Table: N (%) with any of medications listed prescribed before admission [Y/N] and N (%) for each medication, by treatment arm, and overall.

4.3 Trial treatment details, and adherence

No formal statistical testing will be performed.

The protocol defines:

Crossover Any patient in the control group that has a CTCA as part of routine care within 30 days of randomisation will be defined as a crossover and does not need to be recorded as a deviation.

Non-adherence This will be defined as to have occurred in any participant not receiving a reported CTCA if randomised to it within 72 hours of the randomisation and this would be recorded as a deviation. This allows ambulatory CTCA to be delivered when appropriate.

Non-adherence

Table: For those allocated to the CTCA arm, the number of patients who received the allocated treatment within 72 hours of randomisation, later than 72 hours, or not at all. Only those who received CTCA within 72 hours of randomisation received the treatment as allocated.

Table: For those allocated to the CTCA arm, who did not receive CTCA as the trial intervention, reasons for not receiving CTCA as trial intervention

Histogram: For patients allocated to CTCA arm, time from randomisation to receiving CTCA as trial intervention

Crossover

Table: For those allocated to the control arm, the number of patients who did not receive CTCA during trial, who did receive CTCA more than 30 days after randomisation, or who received CTCA within 30 days of randomisation. Those who received CTCA within 30 days are crossovers.

Trial treatment details

Table: For those allocated CTCA, who received CTCA, a table showing the following: scan quality, inpatient or ambulatory scan appointment, type of scan [e.g. prospective, retrospective, flash], beta blocker administered [Yes, No], GTN administered [Yes, No], number of detectors/slices.

4.4 Primary outcome

The primary outcome will be all-cause death or subsequent non-fatal type 1 or type 4b MI at one year, measured as time from randomisation to first such event. MI will be defined according to the most recent Universal Definition [3] and will be adjudicated by two independent cardiologists blinded to the intervention. Patients discontinuing the study (for any reason) prior to reaching primary outcome

will have their time to primary outcome censored at the last contact date. The level of missing data is low, so a multiple imputation analysis for missing data is not necessary.

Primary analysis

If the proportional hazards assumption holds, using visual inspection, then the relationship between intervention and the primary outcome will be analysed using Cox proportional hazard regression. The results will be expressed as a hazard ratio with the corresponding 95% confidence intervals and p-value. The primary analysis will be adjusted as specified in the Overall Statistical Principles section of this document. An unadjusted analysis will also be presented, as a sensitivity analysis.

If the adjusted analysis p-value is <0.05 , this will be declared as a statistically significant p-value, and formal statistical testing will continue to the key secondary outcomes. If the adjusted p-value is not <0.05 , formal statistical testing of outcomes will stop at this point, and further p-values will be presented for information only.

The number of patients with an outcome event (by treatment group) will be tabulated, and the following statistics will be presented: adjusted HR (and 95% CI, p value), unadjusted HR (and 95% CI, p value). A Kaplan-Meier plot will be produced, showing results by allocated treatment - The p-value on the plot will be the p-value from the adjusted Cox regression analysis above..

A tabulated of the individual elements of the composite primary outcome will be produced – this table will specify whether each patient's primary outcome was death or MI.

Subgroup analysis

Subgroup analysis on the primary outcome is planned for age ($<65/\geq 65$ years), sex (Male/Female), baseline GRACE score (grouped as <109 , 109-139, 140 or more), previous CAD (Y/N), baseline ECG result (normal/abnormal), baseline troponin concentration (initial measurement above/below the 99th centile for the site-preferred assay – sex specific where available), and presentation to a study site with or without on-site invasive coronary angiography facilities.

These will be assessed by examining the effect of entering the treatment by subgroup interaction into the Cox regression model. The ratio of hazard ratios, plus 95% confidence interval, will be given for the interaction. Within subgroup treatment effect estimates and confidence intervals will also be presented. If time allows, this will be presented as a forest plot.

We will also prepare a table or graph of effect size by centre for the primary outcome, for the 5 largest sites (all randomised >100 patients). This will not involve any formal statistical testing.

4.5 Key secondary outcomes

1. Coronary Heart Disease (CHD) death or subsequent non-fatal MI;
2. Cardiovascular Disease (CVD) death or subsequent non-fatal MI;
3. Subsequent Non-fatal MI;
4. Coronary Heart Disease death;
5. Cardiovascular death;
6. All-cause death.

These outcomes are measured as the time from randomisation to the first relevant event. Patients discontinuing the study (for any reason) prior to reaching the relevant outcome will have their time to outcome censored at the last contact date. Patients who die from a cause that is not part of the relevant outcome, before achieving the relevant outcome, will have their time to outcome censored at the date of death.

The analysis will use adjudicated outcome data, where these are available and relevant.

If the proportional hazards assumption holds, using visual inspection, then the relationship between intervention and each key secondary outcome will be analysed using Cox proportional hazard regression. The results will be expressed as a hazard ratio with the corresponding 95% confidence intervals and p-value. The primary analysis will be adjusted as specified in the Overall Statistical Principles section of this document. An unadjusted analysis will also be presented, as a sensitivity analysis.

The number of patients with an outcome event (by treatment group) will be tabulated, and the following statistics will be presented: adjusted HR (and 95% CI, p value), unadjusted HR (and 95% CI, p value). A Kaplan-Meier plot will be produced, showing results by allocated treatment. If the adjusted p-value from the primary outcome is <0.05 , then formal statistical testing will continue into the key secondary outcomes. If this is the case, for each key secondary outcome in turn, in the order as listed above, an outcome will be declared as a statistically significant if the adjusted p-value <0.05 , and if this is so, then formal statistical testing will continue to the next outcome in the list. If the adjusted p-value is not <0.05 , formal statistical testing of outcomes will stop at this point, and further p-values will be presented for information only.

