Patients will be followed up using routine clinical notes and research contact with the patient by phone, email or post. A 3% loss to follow up (patient withdrawal and inability to retrieve data for the primary outcome from routine NHS records) is built into the sample size calculation for the primary outcome; all patients will be analysed for the primary outcome on an intention-to-treat basis. At Trusts where it is not possible to routinely get this data from the NHS records, the research team at site will attempt to contact the participant and/or their GP by telephone to gather the 12-month follow up data. All patients will be followed for 1 year.

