4.6 Other secondary outcomes

Any p-values presented will be for descriptive purposes only, and should not be considered as formal statistical significance testing.

1. Coronary Heart Disease (CHD) death or subsequent non-fatal MI (type 1 or 4b);

This will be measured as the time from randomisation to the first relevant event. Patients discontinuing the study (for any reason) prior to reaching the outcome will have their time to outcome censored at the last contact date. Patients who die from a cause that is not part of the outcome, before achieving the outcome, will have their time to outcome censored at the date of death.

The analysis will use adjudicated outcome data, where these are available and relevant.

If the proportional hazards assumption holds, using visual inspection, then the relationship between intervention and this outcome will be analysed using Cox proportional hazard regression. The results will be expressed as a hazard ratio with the corresponding 95% confidence intervals and p-value. The primary analysis will be adjusted as specified in the Overall Statistical Principles section of this document. An unadjusted analysis will also be presented, as a sensitivity analysis.

The number of patients with an outcome event (by treatment group) will be tabulated, and the following statistics will be presented: adjusted HR (and 95% CI, p value), unadjusted HR (and 95% CI, p value). A Kaplan-Meier plot will be produced, showing results by allocated treatment.

2. Subsequent Non-fatal MI (type 1 or 4b);

This will be measured as the time from randomisation to the first relevant event. Patients discontinuing the study (for any reason) prior to reaching the outcome will have their time to outcome censored at the last contact date. Patients who die from a cause that is not part of the outcome, before achieving the outcome, will have their time to outcome censored at the date of death.

The analysis will use adjudicated outcome data, where these are available and relevant.

If the proportional hazards assumption holds, using visual inspection, then the relationship between intervention and this outcome will be analysed using Cox proportional hazard regression. The results

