will be expressed as a hazard ratio with the corresponding 95% confidence intervals and p-value. The primary analysis will be adjusted as specified in the Overall Statistical Principles section of this document. An unadjusted analysis will also be presented, as a sensitivity analysis.

The number of patients with an outcome event (by treatment group) will be tabulated, and the following statistics will be presented: adjusted HR (and 95% CI, p value), unadjusted HR (and 95% CI, p value). A Kaplan-Meier plot will be produced, showing results by allocated treatment.

3. Non-cardiovascular death;

This will be measured as the time from randomisation to the first relevant event. Patients discontinuing the study (for any reason) prior to reaching the outcome will have their time to outcome censored at the last contact date. Patients who die from a cause that is not part of the outcome, before achieving the outcome, will have their time to outcome censored at the date of death.

If the proportional hazards assumption holds, using visual inspection, then the relationship between intervention and this outcome will be analysed using Cox proportional hazard regression. The results will be expressed as a hazard ratio with the corresponding 95% confidence intervals and p-value. The primary analysis will be adjusted as specified in the Overall Statistical Principles section of this document. An unadjusted analysis will also be presented, as a sensitivity analysis.

The number of patients with an outcome event (by treatment group) will be tabulated, and the following statistics will be presented: adjusted HR (and 95% CI, p value), unadjusted HR (and 95% CI, p value). A Kaplan-Meier plot will be produced, showing results by allocated treatment.

4. Invasive coronary angiography;

This will be measured as the time from randomisation to the first relevant event. Patients discontinuing the study (for any reason) prior to reaching the outcome will have their time to outcome censored at the last contact date. Patients who die before achieving the outcome, will have their time to outcome censored at the date of death.

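### Kaplan-Meier curves that censor deaths are planned for 13 outcomes; read as absolute risk they can only equal or exceed the true cumulative incidence, by a small amount

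*SAP*

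**What the plan says.** SAP 4.5 defines the key secondary outcomes as times to first event. It singles out "Patients who die from a cause that is not part of the relevant outcome, before achieving the relevant outcome" and says that they "will have their time to outcome censored at the date of death". It then plans Cox regression and a plot: "A Kaplan-Meier plot will be produced, showing results by allocated treatment". The rule affects outcomes 1 to 5. Outcome 6, all-cause death, has no death outside it.

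SAP 4.6 repeats the pattern. Items 1 to 3 cover "Patients who die from a cause that is not part of the outcome, before achieving the outcome". Items 4 to 7 (angiography, revascularisation and its two types) and item 11 (re-presentation or rehospitalisation) censor every prior death: "Patients who die before achieving the outcome, will have their time to outcome censored at the date of death". Each of these eight items carries the same plot sentence. The total is 5 + 8 = 13 outcomes.

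For each outcome the SAP also says "The number of patients with an outcome event (by treatment group) will be tabulated", next to the adjusted and unadjusted hazard ratios. Follow-up is fixed: "All patients will be followed for 1 year" (Protocol 5.4.2, Follow up). Neither document, as available, mentions competing risks or cumulative incidence functions.

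**The concern.** Kaplan-Meier treats a censored patient as someone who could still have the event later. That is reasonable for a patient lost to follow-up. It is wrong for one who has died, who cannot later have an infarction, an angiogram or a readmission. One minus the Kaplan-Meier estimate then answers a hypothetical question, namely what share would have the event if nobody died of other causes. It does not give the share of patients who actually have it.

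These plots are the only planned display of absolute risk over time for the 13 outcomes. Several of the outcomes serve the first two secondary objectives in Protocol 2.1.2: use of angiography and revascularisation, and re-presentation. The excess depends on competing mortality, so it could differ between arms if CTCA changes mortality.

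**Working it through.** **Direction.** At each event time tᵢ let dᵢ be the number of events and nᵢ the number at risk.

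- Kaplan-Meier with deaths censored: F_KM = Σ S_KM(tᵢ−)·dᵢ/nᵢ, where S_KM falls only at events.
- Aalen-Johansen: F_AJ = Σ S_all(tᵢ−)·dᵢ/nᵢ, where S_all falls at events and at competing deaths.

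S_KM is never below S_all, and the two are equal until the first competing death. So F_KM ≥ F_AJ, and the curves part at the first event that follows a competing death. In 1,500 simulated arms (868 patients each, 3.4% competing mortality, true incidence 5%, 20% or 46%), F_KM was never below the observed proportion.

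**Inputs from the documents.**

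- Primary event rate 6.8% (95% CI 5.2% to 8.9%) in the first 716 participants (Protocol 4.1). This is the pooled rate: 8.5% v 5.1%, which averages 6.8% and differs by 3.4 points, gives 860 per arm at 80% power and two-sided 5% (pooled variance, no continuity correction). That is the stated 1,720. Taking 6.8% as the control rate gives 1,314.
- Angiography 46% and revascularisation 20%, from the background cohort in Protocol 1.1. These are not this trial's data.
- About 868 per arm (1,735 / 2).

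**Assumptions.** The documents give no mortality for this trial and no event rates for these 13 outcomes. I take constant hazards, and 3% to 5% dying before the event where no bound is available.

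**Formula.** Let e be the true one-year incidence and d the proportion dying of a competing cause before the event. The total hazard is −ln(1 − e − d), the event hazard is λ = [−ln(1 − e − d)]·e/(e + d), and the excess is (1 − exp(−λ)) − e.

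**Five outcomes bounded by the primary composite.** For CHD death, cardiovascular death and non-cardiovascular death, event plus competing death is total mortality. For the two type 1/4b MI outcomes (SAP 4.6 items 1 and 2), event plus competing death cannot exceed the primary composite. The excess is largest near an even split.

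- At 6.8%: e = d = 3.4%, λ = 0.07042/2 = 0.03521, curve 3.46%, excess **0.06 points**.
- At 8.9%: e = d = 4.45%, λ = 0.04661, curve 4.55%, excess **0.10 points**.

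These maxima hold under constant hazards. If every competing death came before every event, the excess would be e·d/(1 − d) = 0.034 × 0.034/0.966 = 0.12 points at 6.8%.

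**Key secondary outcomes 1 to 3.** These use MI of any type, so the bound does not apply. At an illustrative e = 5%, the excess is 0.08 points (d = 3%) to 0.13 points (d = 5%).

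**Procedures and re-presentation.**

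| e | d | λ | Curve | Excess (points) |
|---|---|---|---|---|
| 20% | 3% | 0.2273 | 20.33% | 0.33 |
| 20% | 5% | 0.2301 | 20.56% | 0.56 |
| 46% | 3% | 0.6321 | 46.85% | 0.85 |
| 46% | 5% | 0.6434 | 47.45% | 1.45 |

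Constant hazards are pessimistic for procedures. CTCA is due within about 72 hours (Protocol 5.4.2), and Appendix 1 sends obstructive disease to angiography. If, as an assumption, 80% of angiograms fall in the first 14 days, the 46% rows become 0.28 and 0.48 points.

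**Difference between arms.** Take an assumed 30% incidence in both arms with d = 5% v 3%. The excesses are 0.87 and 0.52 points, a false gap of 0.36 before rounding. The standard error of the difference is √(2 × 0.30 × 0.70/868) = 2.2 points, so the artefact is about one sixth of it.

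**The case against.** The strongest reply is that nothing the trial will estimate or test is touched. The listed results are event counts and hazard ratios with confidence intervals and p-values. The SAP plans no Kaplan-Meier percentage at one year, no risk difference from the curves and no log-rank test. Censoring competing deaths in a Cox model gives a valid cause-specific hazard ratio. The tabulated counts already show the crude share with each event, and the p-values for the eight outcomes in SAP 4.6 are descriptive. All of this stands, and it makes the point one of presentation.

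Stronger readings are tempting, but the documents do not support them:

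- *Every curve is wrong.* In an arm where no competing death precedes a later event, the curve is exact.
- *The hazard ratios or the hierarchy are compromised.* They are not, for the reasons above.
- *Part of the visible gap between arms is an artefact.* In principle yes, but the illustration gives about 0.36 points against a standard error of 2.2, which nobody would see on a plot.
- *Mortality cannot exceed 6.8%.* That figure is a pooled estimate from 716 participants and bounds neither final nor per-arm mortality. The calculation at 8.9% also covers the 8.5% arm rate implied by the sample size.
- *A mismatch with the counts proves the error.* Loss to follow-up also separates curves from crude counts, under either method.

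The SAP does not say whether survival or its complement will be plotted. The point therefore concerns any absolute risk read from the curve.

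**Conclusion.** The point holds as a minor one. For 13 outcomes the planned curve, read as absolute risk, can only err upwards, and it does so whenever a competing death precedes a later event in that arm. Nothing elsewhere in the documents corrects this.

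The likely size runs from under a tenth of a point for the cause-specific death and type 1/4b MI outcomes to around one point for angiography, with the lower end more plausible where procedures come early. These sizes rest on constant hazards, an assumed 3% to 5% dying before the event, and procedure rates borrowed from a background cohort. No hazard ratio, p-value, event count, sample size or hierarchy decision changes. The primary outcome and all-cause death have no competing death and are unaffected.

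**What to change.** For key secondary outcomes 1 to 5 and SAP 4.6 items 1 to 7 and 11, replace the Kaplan-Meier plot with Aalen-Johansen cumulative incidence curves by arm, treating death that is not part of the outcome as a competing event. Keep the cause-specific Cox model as the estimate and test. Keep Kaplan-Meier for the primary outcome and all-cause death.

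The plot sentence needs editing in nine places: once in SAP 4.5, with all-cause death exempted, and once in each of the eight affected items in 4.6. The cost is minor reprogramming with a standard SAS option and slightly lower plotted percentages. No power is lost.
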